3.3. Research Approach

3.3.a Research Design Overview. We will conduct a randomized controlled trial, where upon enrollment participants will be randomized to either the *Guerreiras* intervention or to a wait-list control condition, in which participants will also receive the *Guerreiras* intervention after a one-year waiting period. We chose a wait-list control to safeguard ethical treatment of participants by ensuring that a potentially impactful intervention will be available to all after a brief waiting period. Rolling enrollment of 400 participants will take place over one year, with the intervention initiating activities as participants are assigned to a *Guerreiras* group (8-10 participants); group assignment will occur as soon as sufficient participants are enrolled. *Guerreiras* includes five group sessions over the course of 6-8

weeks, led by two peer navigators (PNs). Following group sessions, PNs will provide six months of peer navigation to each participant to support HIV testing (clinic or HIVST), PrEP uptake and persistence, harm reduction and other behavioral prevention as indicated, or HIV care (if participant tests positive). Groups will reconvene for a reunion session 3 months into navigation services (see Intervention Design 3.4). Follow-up data collection for the main

Figure 2: Study Design

trial phase will be conducted every three months, with comprehensive interviewer-administered surveys conducted at enrollment (baseline), 6 months (interim survey), and 12 months (endline), with brief monitoring surveys at the 3-month visits (e.g. 3- and 9-months) to assess prevention uptake (HIV testing, PrEP use, etc; see Figure 2, Study Design). This results in four post-enrollment follow-up visits per participant to document regular prevention uptake and two visits to document changes in stigma measures during the main trial phase. Qualitative interviews will be conducted with 18 participants at two timepoints (36 interviews total) to provide context to our exploration of intersectional stigma and gender affirmation, including how intersectional stigma impacts engagement with *Guerreiras* and HIV prevention uptake, how gender affirming programming impacts intersectional stigma, and insight into psychosocial mechanisms of change over time.

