3.7 Measures

Primary Exposure: Randomization arm – intervention or wait-list control – will be considered the primary predictor variable for all primary analyses and recorded on study enrollment forms. Because the degree of engagement with the intervention will vary by individual, we will also capture intervention dose on study monitoring forms as a secondary exposure measure for additional (per protocol) analyses.

Primary Outcomes: (Evaluation: Aims 1 & 2): HIV testing uptake will be defined as any clinical evidence or report of HIV testing in each interval. This includes multiple data sources: documented HIV testing at a study clinic, report of having attended a non-study clinic for HIV testing, or evidence of HIVST kit receipt with self-report of HIVST use and/or documented HIVST use by the PN during a group or individual navigation session. The primary PrEP use outcome measure is PrEP *persistence*, which is the PrEP measure utilized for sample size calculations. We will document *PrEP initiation*, defined as a participant filling their first PrEP prescription, through PrEP dispensing information in the national SICLOM database. However, because initiation does not imply continued use, we will focus analyses of PrEP use on *PrEP persistence* – or documented use at every interval, defined as sufficient pill dispensation for complete 3-month coverage with no more than 10 days uncovered in the period. Secondary outcomes, including PrEP *adherence* and uptake of other prevention services (harm reduction, STI care) are listed in Table 3, below.

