Mediators: Intersectional Stigma: We will include a comprehensive suite of stigma measures that will be examined together in mediation and moderation analyses (see Analysis section 3.8). To explore the concept of intersectional stigma, we will analyze potential interactions between the stigma domains. This reflects the concept of intersectionality as more than an additive process of multiple stigmatized identities, but where experiences of multiple types of stigma create a confluence of interlocking systems of oppression that act synergistically as barriers to prevention and cannot be meaningfully interpreted independently. We will include quantitative measures of internalized, anticipated, and enacted stigma in the following domains: gender-related stigma, race-related stigma, stigma related to sex work and substance use, HIV and PrEP stigma. Stigma resilience is operationalized as coping self-efficacy and healthcare empowerment in the context of anticipated

and enacted stigma. Comprehensive surveys will be conducted at enrollment, interim, and endline at 6-month intervals; we do not expect changes in stigma every 3 months (interval for outcomes monitoring).

Covariates: We will measure demographic and other individual, social, and structural barriers or facilitators to care to assess potential covariates and confounders in analyses.

Table 3: Primary and Secondary Measures

Domain	Instrument/measure	Data source	Frequency of data collection/extraction
PRIMARY EXPOSURE			
Intervention	Randomization arm	Enrollment/study records	Continuous during enrollment
PRIMARY OUTCOMES			
HIV testing	Binary: Tested (HIVST or at a clinic) in past 3-months	Clinical data extraction; study records (HIVST); self-report (testing)	Extracted bi-annually, Continuous, Monitoring visits (3-monthly)
PrEP initiation	Binary: Initiation of PrEP in past 3-months*	National data (SICLOM)	Extract quarterly
PrEP persistence	Binary: PrEP dispensed with 80 or more days covered in 3-months per dispensation records*	National data (SICLOM)	Extract quarterly
SECONDARY OUTCOMES			
Prevention and service uptake	Uptake of harm reduction services	Self-report	Monitoring visits (3-monthly)
	STI referrals and treatment	Clinical data extraction; Self-report	Extracted bi-annually, Monitoring visits (3-monthly)
	Condom use (consistent use with regular and occasional partners and clients)	Clinical data extraction; Self-report	Extracted bi-annually, Monitoring visits (3-monthly)

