Primary analyses for Aims 1 and 2. We expect HIV prevention outcomes to improve in the intervention arm relative to the control arm during the main trial phase. We hypothesize that, following the intervention, odds of HIV testing will be higher for intervention participants relative to control participants (Aim 1, Hypothesis 1). We also hypothesize that, following the intervention, the odds of PrEP initiation and persistence will be higher for the intervention group than for the control group (Aim 2, Hypothesis 2). Our primary interest is to estimate the marginal or population-average effects of intervention participation on these primary outcomes rather than the effect for a hypothetical average subject¹²⁶. Moreover, within-subject outcome correlations are considered nuisance parameters rather than quantities of interest to be modeled explicitly. Accordingly, generalized estimating equations (GEE) will be used for the primary analyses to test Hypotheses 1 and 2 using time-averaged comparisons of post-baseline (follow-up) measurements of intervention group with control group in the main trial phase. Alpha (α) will be set at .05 for these two planned comparisons. The alternating logistic

regression (ALR) approach implemented in SAS PROC GENMOD will be used to address the 3-level clustering of observations within participants and participants assigned to *Guerreiras* group leaders. This analysis will follow an intent-to-treat (ITT) approach by including all randomized participants. Further detail on the analytic model and secondary analyses, including secondary outcomes, intervention persistence, and intervention replicability, are included in Form E, Statistical Design and Power.

Primary Analyses for Aim 3. GEE will be used to test Aim 3 hypotheses that, following the intervention, relative to the control arm, intervention arm participants will have: 1) higher mean levels of resilience to anticipated stigma, 2) higher mean levels of resilience to enacted stigma, and 3) lower mean levels of internalized stigma. Analyses will follow the same ITT modeling approach as described above for Aims 1 and 2, except that a normal distribution and identity link will be employed to analyze continuous, normally-distributed stigma scores. These hypotheses will be tested via planned time-averaged comparisons of post-baseline measurements of the two arms in the main trial phase. These comparisons will be tested at $\alpha=.05$ per comparison.

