We will also explore whether stigma measures at interim (six-months) surveys mediate the relationship between intervention assignment and subsequent outcomes as well as whether combinations of stigmas measures at baseline and six-months act synergistically (interact) and moderate the exposure-outcome associations in order to assess intersectional stigma. We will also assess whether measures of gender affirmation and transgender group identity increase over the course of the intervention and mediate the relationship between intervention arm and subsequent outcomes. Further detail on Aim 3 secondary analyses, including mediation and moderation, are in Form E, Statistical Design and Power.

Statistical power. We computed minimum detectable effect sizes for primary outcomes using the two-group repeated proportions module in NCSS PASS 16¹²⁷. The study will begin with 400 participants equally allocated to two study groups. Assuming 25% attrition, data from 300 participants will be available for analysis at all time points. We further lowered the effective sample size (ESS) to account for correlations between participants receiving the intervention from the same *Guerreiras* PN pairs, using a range of plausible intraclass correlations (ICC)s within PN pairs. Assuming $\alpha=.05$ and $\text{power}=.80$, with four post-baseline measurements and assuming control group proportions $P_0=.50$ for HIV testing and $P_0=.05$ for PrEP use, we will have sufficient power to detect small to medium effects. This includes effects as low as 13% and 8% difference in proportion in HIV testing and persistent PrEP use, respectively, in the intervention arm compared to control. Effect size estimates for primary analyses (all Aims 1, 2, and 3) fall between cutoffs of .20 and .50 for small and medium standardized effect sizes¹²⁸. Statistical power is fully elaborated in Form E, Statistical Design and Power.

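### Six-month stigma, which the intervention is meant to change, is planned as a moderator of the arm effect, so those arm contrasts are not randomised comparisons

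*Combined protocol and SAP*

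**What the plan says.** Section 3.7 fixes the exposure: "Primary Exposure: Randomization arm". It also gives the stigma scales two roles, as a "comprehensive suite of stigma measures that will be examined together in mediation and moderation analyses".

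Section 3.8 (Primary Analyses for Aim 3) hypothesises that, after the intervention, the intervention arm will have greater resilience to anticipated and enacted stigma and "lower mean levels of internalized stigma". It then lists exploratory work. One part asks whether "stigma measures at interim (six-months) surveys mediate the relationship between intervention assignment and subsequent outcomes". The other part, in the same sentence, asks "whether combinations of stigmas measures at baseline and six-months act synergistically (interact) and moderate the exposure-outcome associations".

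On timing, section 3.3.a places the stigma surveys at enrolment, 6 months and 12 months. The five group sessions take 6 to 8 weeks, and then "Following group sessions, PNs will provide six months of peer navigation to each participant". Delivery is therefore well under way at the six-month survey.

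The detailed specification is held elsewhere: "Further detail on Aim 3 secondary analyses, including mediation and moderation, are in Form E, Statistical Design and Power". Form E is not part of the document under review.

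**The concern.** A moderator of a randomised effect should be fixed before randomisation, or at least be unaffected by arm. On the plan's own hypotheses, six-month stigma is neither. If the intervention lowers stigma, the women with low six-month scores in the intervention arm include some who would have scored high without it. Their control counterparts scored low unaided. The two groups then differ on whatever else drives stigma, and if that also drives testing or PrEP use, the arm contrast within the stratum mixes the intervention effect with selection.

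Such common causes are plausible here. Table 3 lists depression, substance use, trauma, social support and food insecurity among the barriers to and facilitators of prevention.

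At stake is an exploratory answer to a question the protocol presents as novel (section 3.2): how stigmas in combination alter uptake. A report that the intervention works better in low-stigma or high-stigma women could reflect selection, and a real difference could be hidden.

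There is also a matter of order in time. The mediation clause is limited to outcomes after six months, but the moderation clause is not. As written, six-month stigma could be used to moderate the month-3 outcome, which precedes it.

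**Working it through.** **1. Is the moderator affected by arm?** Set side by side, the texts give: exposure = arm (3.7); arm is expected to change stigma after baseline (3.8); six-month stigma is a mediator of arm (3.8); six-month stigma, with baseline stigma, is a moderator of the exposure-outcome association (3.8). The last two roles conflict for the six-month score. They do not conflict for the baseline score.

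**2. Inputs for size.** The plan gives no figure for the moderation analysis, so there is none to reproduce. From section 3.8: control proportion .50 for HIV testing, a detectable difference of 13 points, and 400 × (1 − .25) = 300 analysable. Everything else is assumed:

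- Baseline stigma S0 and an unmeasured cause U are independent standard normal variables.
- Six-month stigma: S6 = .5·S0 − .5·A + .6·U (± .3·A·U) + noise with SD .6. Its SD in the control arm is √(.25 + .36 + .36) = .98, so the arm shift is about half an SD.
- Outcome: logit(Y) = .53·A ± .8·U. The .53 is ln(.63/.37) − ln(.50/.50), the plan's 13-point difference. Averaged over U it becomes about 11.4 points.
- There is no true moderation, one outcome per woman and no clustering by navigator pair.

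**3. Arm effect (points) within median halves of six-month stigma; true value about 11.4**

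| U raises stigma and… | Shift in stigma | Low half | High half |
|---|---|---|---|
| lowers testing | same for all | 7.7 | 8.6 |
| lowers testing | varies with U (−.3) | 4.6 | 12.3 |
| raises testing | same for all | 15.3 | 14.2 |
| raises testing | varies with U (−.3) | 18.4 | 10.5 |

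Repeat runs agree to within a few tenths of a point. Halves of **baseline** stigma give 11.3 to 11.6 points.

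The first two rows fit the protocol's account better, since section 3.1 links stigma to avoidance of care and low testing. The sign of the bias still depends on a cause that nobody has measured.

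**4. False interaction at n = 300.** With a uniform shift, rejection is near the nominal 5%. With the −.3 term it is about 9 to 10%. With a +.3 term it is about 4 to 6%. With baseline stigma it is 4 to 6%.

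A hand check shows why the excess is modest. With about 300/4 = 75 women per cell and variance near .25, the standard error of the difference between the two arm effects is √(4 × .25/75) = .115. The spurious gap in the second row is 12.3 − 4.6 = 7.7 points, and .077/.115 = .67. Rejection is then about P(Z > 1.29) + P(Z < −2.63) = .099 + .004 = .10. The uniform-shift gap is 8.6 − 7.7 = 0.9 points, too small to move the test. The main harm is in the estimates.

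**5. A second, differently built model.** Here the true effect is 13 points for everyone, U lowers the outcome by 10 or 15 points per SD, and the outcome is the mean of two later visits.

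- Uniform shifts of .2 to .5 SD: 9.6 to 12.0 points in the six-month halves, with 5.1 to 5.4% rejection.
- Mean shift of .35 SD, larger in high-U women: from 9.8 v 13.4 points (extra .3 SD per SD of U, 10-point U effect) to 6.0 v 16.1 (extra .5, 15-point U effect). Rejection is 5.7 to 7.3% with the extra .3 and 12 to 20% with the extra .5.
- Baseline halves: 12.8 to 13.2 points, with 4.8 to 6.6% rejection.
- No effect of arm on stigma: no bias.

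**The case against.** **The analysis is exploratory and its specification is in Form E.** Both are true. Form E may place an arm-by-mediator interaction inside a causal mediation model, which would be acceptable. But the rule stated in section 3.8 is moderation of the arm effect by six-month scores, with no safeguard, and a pointer to another document does not cancel it.

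**The sentence is partly about stigma-by-stigma synergy.** Section 3.7 speaks of interactions between stigma domains. That part need not involve an arm contrast within six-month strata, and it need not be barred. The objection stands to that extent. The sentence nevertheless goes on to moderation of the exposure's association with outcome.

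**A reader might infer that the bias inflates subgroup effects, or that false moderation is to be expected.** The documents support neither. Inflation requires the hidden cause to raise both stigma and testing, against the direction described in section 3.1; the opposite sign gives attenuation. A uniform shift produces no excess of false interactions.

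**A reader might infer that the whole assessment of intersectional stigma rests on these models.** It does not. Aim 3 has its own randomised GEE comparisons, and the longitudinal interviews address the same question.

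**Moving six-month stigma into the mediation model does not remove confounding.** This is correct. The same unmeasured cause confounds the mediator-outcome path, and adjusting for baseline stigma alone does not remove it. The remedy therefore needs measured common causes and a sensitivity analysis as well.

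**Conclusion.** The point holds for one exploratory Aim 3 analysis. Arm effects estimated within levels of six-month stigma are not protected by randomisation, because the plan itself expects arm to change those scores. Bias follows if arm shifts stigma and some cause is shared by stigma and outcome.

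Under the assumed inputs, a true effect of about 11.4 points appears as about 8 to 9 in both halves, or 14 to 15, depending on the sign of that cause. A spurious difference between halves needs arm's effect on stigma to vary between women. The false interaction rate is then about 9 to 10% in the adverse scenario of the main model, and it reaches 12 to 20% only in the second model's strongest settings. Otherwise it is near 5%. No figure in the documents fixes these inputs, so the sizes are illustrative; what is firm is that the direction cannot be known in advance. If arm does not change stigma, this bias disappears, but the Aim 3 hypotheses would then have failed too.

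The Aim 1 and Aim 2 tests, the three Aim 3 hypothesis tests and the baseline part of the moderation analysis are unaffected. The change should be made, but it does not threaten the trial's main conclusions.

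**What to change.** In section 3.8:

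- Restrict models of moderation of the arm effect to baseline stigma scores and their combinations.
- Use six-month stigma, including stigma-by-stigma and arm-by-mediator interactions, only within the mediation models, and only for outcomes after six months.
- Adjust those models for baseline stigma and for the common causes in Table 3 as measured at baseline. State the no-unmeasured-confounding assumption and add a sensitivity analysis for unmeasured mediator-outcome confounding.
- Label any arm contrast stratified by six-month stigma as descriptive.

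If Form E already does this, bring section 3.8 into line with it.

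The cost is a few sentences and one added sensitivity analysis. No new data are needed, because the baseline survey already collects these scores and covariates. The small loss is that variation in the arm effect by six-month stigma is no longer reported as moderation.
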